4.4. Protocol Deviations

All major protocol deviations will be tabulated and listed, by cohort, by treatment group and overall. Those that may affect the assessment of efficacy will be flagged (see Section 2.3.2.2).

4.5. Medical History and Family History

Reported general medical history conditions will be presented as number (n) and percentage (%) of subjects according to the Medical Dictionary for Regulatory Activities (MedDRA) primary system organ class (SOC) and preferred term (PT). Separate summary tables will be provided for subjects with risk factors for severe RSV disease.

Risk factors for severe RSV disease, general medical history and family records will also be listed.

4.6. Prior and Concomitant Medications

Medications taken from the date when the ICF is signed through the end of study will be summarized by cohort, by treatment group and overall, by preferred term using the World Health Organization-Drug Dictionary as frequency tables for the prior and concomitant medications separately:

1. Prior medication: medication that started before the first dose of study drug, regardless of when dosing of the medication ended.
2. Concomitant medication: medication received at or after the first dose of study drug, medication that was received before initial dosing and continued after initial dosing of study drug, or medication with missing stop date.

Medication that started before the first dose of study drug and continued after the first dose of study drug will be summarized as prior medication and separately as concomitant

medication. The part on concomitant medication will be shown by ATC class level up to level 3. If a prior/concomitant therapy record has missed components of its start and/or stop dates (time and/or day and/or month and/or year), the following actions will be taken:

1. In case of partial start or stop date/times, the concomitant therapy records will be allocated to prior/concomitant using the available partial information, without imputations.
2. In case of a completely missing start date, the prior/concomitant therapy will be considered as having started before the trial.
3. In case of a completely missing end date, the prior/concomitant therapy will be considered as ongoing at the end of the trial.

All prior and concomitant medication will be listed.

In addition, the proportion (number [n] and percentage [%]) of subjects in the ITT-i/Safety analysis set with prior-, concomitant- and any use of medications of special interest will be presented. These include antibiotics, antitussives, bronchodilators, mucolytics, inhaled and systemic corticosteroids according to the following categories:

Prior use only:

Table 13: Prior Use of Medications of Interest

PRIOR USE	NO	YES
Antitussives	No prior use	Any prior use
Bronchodilators	No prior use within the 24h before first dose of study drug	Any prior use within the 24h before first dose of study drug
Mucolytics	No prior use	Any prior use
Inhaled corticosteroids	No prior use or use to a maximum of 2 consecutive days	Prior use for a minimum of 3 consecutive days
Systemic corticosteroids	No prior use or use to a maximum of 2 consecutive days	Prior use for a minimum of 3 consecutive days
Any medications of interest	No prior use	
 • Prior use of only one medication of interest: 
 ○ Antitussives prior use only ○ Bronchodilators prior use only ○ Mucolytics prior use only ○ Inhaled corticosteroids prior use only ○ Systemic corticosteroids prior use only • Prior use of 2 or more medications of interest

Concomitant use only:

Table 14: Concomitant Use of Medications of Interest

CONCOMITANT USE	NO	YES
Antibiotics	No concomitant use	Any concomitant use

CONCOMITANT USE	NO	YES
Antitussives	No concomitant use	Any concomitant use
Bronchodilators	No concomitant use	Any concomitant use
Mucolytics	No concomitant use	Any concomitant use
Inhaled corticosteroids	No concomitant use	Any concomitant use
Systemic corticosteroids	No concomitant use	Any concomitant use
Any medications of interest	No concomitant use	
 • Use of only one concomitant medication of interest: 
 ◦ Antibiotics use only ◦ Antitussives use only ◦ Bronchodilators use only ◦ Mucolytics use only ◦ Inhaled corticosteroids use only ◦ Systemic corticosteroids use only • Use of 2 or more concomitant medications of interest

Any use (prior and/or concomitant):

Table 15: Any Use of Medications of Interest

ANY USE	NO	YES
Antibiotics	No prior and/or concomitant use	Any prior and/or concomitant use
Antitussive	No prior and/or concomitant use	Any prior and/or concomitant use
Bronchodilators	No prior and/or concomitant use	Any prior and/or concomitant use
Mucolytics	No prior and/or concomitant use	Any prior and/or concomitant use
Inhaled corticosteroids	No prior and/or concomitant use	Any prior and/or concomitant use
Systemic corticosteroids	No prior and/or concomitant use	Any prior and/or concomitant use
Any medications of interest	No prior and/or concomitant use	
 • Use of only one prior and/or concomitant medication of interest: 
 ◦ Antibiotics use only ◦ Antitussives use only ◦ Bronchodilators use only ◦ Mucolytics use only ◦ Inhaled corticosteroids use only ◦ Systemic corticosteroids use only • Use of 2 or more prior and/or concomitant medications of interest

Prior and/or concomitant medications of interest: incorporate the defined use of medications of interest as detailed in [Table 13](#) and [Table 14](#) above.

4.7. Respiratory Pathogens

Positive/negative results for identified non-RSV pathogens at baseline, as based on respiratory pathogens assay, will be presented by the following categories:

- Presence of other respiratory pathogens
- Presence of other respiratory viruses
- Presence of respiratory bacteria

Within each category, number (n) and percentage (%) of subjects with positive/negative results per pathogen will be summarized by cohort, by treatment group and overall. In case multiple results are available from multiple assays per pathogen, the subject will be considered positive for the specific pathogen if one or more results from the multiple assays are positive. For example, for *Bordetella pertussis*: at least two results may be available, one from the Pathofinder Respifinder 2SMART assay and one from the Fast Track Diagnostics *Bordetella* assay. If either or both results are positive, the subject will be considered positive for the presence of *Bordatella pertussis*.

5. EFFICACY

The efficacy analyses include the following primary, secondary and exploratory endpoints.

Primary Endpoint

The primary efficacy endpoint is the RSV viral load AUC from immediately prior to first dose of study drug through Day 5 derived from the RSV viral load as measured by a qRT-PCR assay in nasal swabs.

Secondary Endpoints

- virologic parameters derived from the RSV viral load as measured by a qRT-PCR assay in nasal swabs including:
 - RSV viral load and change from baseline over time
 - RSV viral load AUC from immediately prior to first dose of study drug (baseline) through Day 3, Day 8, and Day 14
 - time to undetectable RSV viral load
 - proportion of subjects with undetectable RSV viral load at each timepoint throughout the study
- clinical course related endpoints:
 - in hospitalized subjects and outpatients:
 - following endpoints will be based on the Pediatric RSV Electronic Severity and Outcome Rating System (PRESORS) assessed throughout the study by parent(s)/caregiver(s) (parent[s]/caregiver[s] PRESORS) and by the investigator (clinician PRESORS) during scheduled visits:
 - ◆ duration and severity of signs and symptoms of RSV disease
 - ◆ change from baseline in parent(s)/caregiver(s) PRESORS scores (worsening or improvement)

- ◆ change from baseline in clinician PRESORS scores (worsening or improvement)
- ◆ time to resolution (i.e. to none or mild) of RSV symptoms
- ◆ time to improvement based on general questions on overall health
- ◆ proportion of subjects with improvement or worsening of RSV disease based on general questions on overall health
- ◆ time to return to pre-RSV health as rated by the parent(s)/caregiver(s)
- respiratory rate, heart rate, body temperature, and peripheral capillary oxygen saturation (SpO₂) over time as measured by the investigator during scheduled visits. **Note:** if the subject is enrolled in the substudy of Study 53718678RSV2002, the same parameters as assessed by the biosensor will be recorded from the standard-of-care monitoring/assessments as part of the substudy assessments.
- body temperature as measured by the parent(s)/caregiver(s) and recorded in the temperature log on the electronic device
- need for (re)hospitalization during treatment and follow-up
- in hospitalized subjects only:
 - time to age-adjusted normal values for otherwise healthy and to pre-RSV infection status for subjects with (a) risk factor(s) for severe RSV disease, for heart rate, respiratory rate, and/or blood oxygen level (i.e. without requirement of supplemental oxygen compared with pre-RSV infection status)
 - time to discharge (from initial admission and from initiation of treatment)
 - time to clinical stability, with clinical stability evaluated by the investigator (from initial admission and from initiation of treatment)
 - need for and duration of intensive care unit (ICU) stay; ‘need for ICU stay’ is defined as follows:
 - ◆ being admitted on the ICU (and ICU level of care is required)
 - ◆ being admitted on the hospital ward, with or without supplemental oxygen, but deemed to require ICU level of care (e.g. not transferred to ICU due to bed availability)
 - ◆ requiring ICU level of care is defined by some specific conditions:
 - acute or imminent respiratory failure
 - treatment of complicated acid-base or electrolyte imbalances
 - cardiogenic shock
 - acute congestive heart failure
 - hemodynamic instability
 - ◆ having other conditions requiring specialized equipment and/or staff competencies only available in the ICU
 - need for and duration of supplemental oxygen (regardless of method used); ‘need for supplemental oxygen’ is defined by:

- ◆ requiring invasive mechanical ventilation
- ◆ receiving any oxygen support requiring intubation or extracorporeal oxygenation
- ◆ receiving invasive mechanical ventilation
- ◆ receiving supplemental oxygen through a face mask or nasal cannula and not being able to sustain a blood oxygen saturation of $\geq 92\%$ when breathing room air for 15 minutes or less, tested once
- need for and duration of non-invasive ventilator support (e.g. continuous positive airway pressure) and/or invasive ventilator support (e.g. endotracheal-mechanical ventilation)
- need for hydration and/or feeding by IV administration or nasogastric tube; need for defined by $<50\%$ of normal oral intake
- time to clinical stability, defined as the time from initiation of study treatment until the time at which the following criteria are met:
 - ◆ return to age-adjusted normal values for otherwise healthy and pre-RSV infection status for subjects with (a) risk factor(s) for severe RSV disease, for all of the following signs/symptoms of RSV disease:
 - heart rate; AND
 - respiratory rate; AND
 - blood oxygen level

AND

- ◆ no more oxygen supplementation for otherwise healthy subjects and subjects with (a) risk factor(s) for severe RSV disease

AND

- ◆ no more IV/nasogastric tube feeding/hydration in otherwise healthy subjects or return to pre-RSV status of IV/nasogastric tube feeding/hydration in subjects with (a) risk factor(s) for severe RSV disease

- time from initiation of study treatment until $\text{SpO}_2 \geq 92\%$ and $\text{SpO}_2 \geq 95\%$ on room air among subjects who were not on supplemental oxygen prior to the onset of respiratory symptoms

- safety and tolerability, as assessed by adverse events (AEs), clinical laboratory testing, electrocardiograms (ECGs), vital signs, throughout the study
- PK parameters of JNJ-53718678, as determined by population PK (popPK) modeling
- medical resource utilization
- acceptability and palatability of the JNJ-53718678 formulation as assessed through a questionnaire completed by parent(s)/caregiver(s) in the electronic device
- sequence changes (post baseline) in the RSV F gene, and other regions of the RSV genome (at the discretion of the sponsor's virologist), as compared with the baseline sequence

Exploratory Endpoints

- The occurrence of complications with onset after treatment initiation that are associated with RSV per investigator assessment:
 - bacterial superinfections (e.g. pneumonia, sinusitis, bronchitis, bacteremia of presumed respiratory origin per investigator assessment)
 - otitis media, bronchiolitis, viral pneumonia
 - exacerbations of underlying pulmonary disease (e.g. asthma, cystic fibrosis, bronchopulmonary dysplasia)
 - exacerbations of underlying cardiovascular conditions
- the use of antibiotics related to complications associated with RSV per investigator assessment
- the RSV RNA viral load as measured by a qRT-PCR assay in nasopharyngeal and/or tracheal aspirate samples in a subgroup of hospitalized subjects in which these samples are obtained as part of their SOC
- comparison of RSV RNA viral load as measured by a qRT-PCR assay in nasal swabs and other samples (e.g. nasopharyngeal and/or tracheal aspirate samples)
- virologic parameters derived from the RSV viral load as measured by quantitative viral culture

5.1. Analysis Specifications

Primary, secondary and exploratory efficacy analyses described in the following sections will be analyzed and presented using primarily the ITT-i analysis set, unless otherwise specified.

Analyses will be performed combining Cohort 1 (hospitalized subjects) and Cohort 2 (outpatients subjects) as well as in each cohort separately except for IA#1 where data from subjects in Cohort 1 only are available. In each IA, the cohort/s information to be considered for decision-making is specified in Section 5.6. For subgroup analysis, please refer to Section 2.4 for further details.

For all the stratified statistical analyses, the derived randomization stratification factors (symptom onset [≤ 3 days vs >3 days to ≤ 5 days before randomization] and presence of risk factors for severe RSV disease [Yes vs No]) will be used instead of the randomization stratification factors as collected in IWRS. Exception is sensitivity analysis of the primary efficacy endpoint based on IWRS randomization stratification factors.

In addition to the analyses outlined in the subsequent sections, efficacy parameters and a selection of derived efficacy variables will be presented in by-subject data listings.

5.1.1. Level of Significance

The primary objective is to establish antiviral activity of JNJ-53718678. The primary efficacy endpoint is the RSV RNA viral load AUC from immediately prior to first dose of study drug through Day 5 ($AUC_{Day\ 5}$) derived from the RSV RNA viral load as measured by a qRT-PCR assay in nasal swabs. A hybrid methodology that combines aspects of multiple testing with modeling techniques (MCP-Mod) will be used for evaluating dose-

response trends and estimating the dose-response relationships. The dose-response will be tested at each (interim) analysis at alpha=2.5% (1-sided).

The primary analysis will only adjust for multiplicity with respect to the candidate models included into the MCP-Mod test. Due to the exploratory nature of the study, no adjustment for multiplicity due to sub-populations and adaptations will be considered in the primary analysis. A secondary analysis approach will be performed to control for multiplicity in the clinical course endpoints and for adaptations (see Section [5.2.3.2](#)).

5.1.2. Data Handling Rules

RSV RNA Viral Load

Rule of maximum: before any imputation is applied, the value for each day is defined as the maximum value of all RSV assessments performed on that day. Please notice that this rule doesn't apply for baseline. For baseline details please see Section [2.1.2](#).

For analysis purposes, the \log_{10} qRT-PCR RSV RNA viral load will be imputed with the midpoint on the log scale between the limit of detection (LOD) and LLOQ of the RSV qRT-PCR assay when the result is 'target detected' (TD) but non-quantifiable.

- For the RSV A qRT-PCR assay, the LOD is 620 copies/mL and the LLOQ is 1000 copies/mL, a result that is TD will be imputed with $2.90 \log_{10}$ copies/mL.
- For the RSV B qRT-PCR assay, the LOD is 80 copies/mL and the LLOQ is 250 copies/mL, a result that is TD will be imputed with $2.15 \log_{10}$ copies/mL.
- When the result is 'target not detected' (TND) (i.e. below the LOD), for both RSV A and RSV B the value of TND will be imputed with $0 \log_{10}$ copies/mL.

For the overall analysis of RSV RNA viral load, all the RSV RNA viral load results of the RSV type with which the subject has been infected will be used.

In case of co-infection with both subtypes RSV A and B, the rules below will be applied for the overall analyses of RSV RNA viral load from the time the co-infection is detected (i.e. result of TD or >LLOQ):

- In case of two quantifiable results: the \log_{10} of the sum of the RSV A and RSV B results in copies/mL will be used.
- In case of a quantifiable result and a TD/TND result: use the imputed TD/TND on the copies/mL scale value and then use the \log_{10} of the sum of the imputed value and the quantifiable result
- In case of two TD results, or one TD and one TND result: use the imputed TD/TND on the copies/mL scale values and then use the \log_{10} of the sum of the imputed values
- In case of two TND results: impute as $0 \log_{10}$.

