5.2.3. Analysis Method

Mean \log_{10} RSV RNA viral load values over time will be analyzed using a restricted maximum likelihood based repeated measures approach (MMRM). The analysis model includes fixed (discrete) effect parameters for treatment, randomization stratification factors (derived), analysis visit and treatment-by-analysis visit interaction, as well as continuous covariates for baseline \log_{10} viral load and baseline \log_{10} viral load-by-analysis visit interaction. An unstructured (co)variance structure will be used to model the within-subject errors. In case this model will not converge, the Toeplitz covariance structure will be applied. The Kenward-Roger approximation will be used to estimate the denominator degrees of freedom.

For subgroup analyses, the model will also include the subgroup variable as a covariate and the subgroup-by-treatment, subgroup-by-analysis visit and subgroup-by-analysis visit-by-treatment interactions. For details about subgroups please see Section 2.4.

A generalized MCP-Mod (1) approach at 1-sided alpha-level of 2.5% will be applied based on the estimated AUC treatment group effect and variance covariance matrix. Candidate models are given by the EMax (0.40428), Exponential (0.36411) and Linear model, with the aim to test for existence of drug-related effects. Each of the dose-response shapes in the candidate set will be tested using the corresponding contrast t-test statistic, employing a critical value derived for the maximum of the t-test statistics (based on the associated multivariate t-distribution) to ensure appropriate multiplicity correction that preserves a 1-sided 0.025 Type I error rate. A dose-response trend is established when the maximum of the t-test statistics exceeds the critical value.

MCP-Mod uses dose levels 0, 3 and 9 mg/kg which correspond to Placebo, Low and High dose respectively according to the dose/kg for age-group 3 as described in Section 1.2.

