RSV RNA viral load status at each timepoint [categorical]	
Each RSV viral load value will be assigned to one of the 3 categories below:
 
 Undetectable (<LLOQ TND) Detectable (<LLOQ TD) Quantifiable (\geq LLOQ) 
Note : in case of co-infection with both RSV A and B, the worst category across subtypes will be used for analysis. Higher RSV viral load denotes worse degree of infection, thus ordering from 'worst to better' follows: Quantifiable – Detectable – Undetectable.
																
RSV RNA viral load status at each timepoint [binary]	
Each RSV RNA viral load value will be assigned to one of the 2 categories:
 
 Detectable or quantifiable = Yes (1) Undetectable = No (0) 
Note : in case of co-infection with both RSV A and B, the worst category across subtypes will be used for analysis. Higher RSV RNA
																

Table 16: Viral Load Parameters

Measurement	Formula
	viral load denotes worse degree of infection, thus ordering from 'worst to better' follows: Quantifiable OR Detectable – Undetectable.

Trapezoidal Method:

The trapezoidal method will be used to calculate RSV RNA viral load AUC between 0 and 312 hours (= Day 14), based on all date/times of viral load sampling, including the timepoints with (imputed) values available:

$$AUC_{0-xx \text{ hours}} = \frac{1}{2} \sum_{i=1}^n (y_i + y_{i-1}) \times (t_i - t_{i-1})$$

where $i=1,2,3\dots$ are the timepoints when post-baseline samples are collected, y_i is the \log_{10} viral load at the time t_i and t_i is the time in hours post-baseline. y_0 is the (imputed) \log_{10} viral load at baseline, t_0 is time 0 hours, t_n is time xx (= 312 hours).

The following rules, will be applied to deal with missing values before calculating the viral load AUC:

1. The value at timepoint 0h, if not exactly at 0h, will be calculated based on linear interpolation between the last observed pre-dose value and the first observed post-dose value.
2. In case the first available observation is after 0 hours, the value at 0h will be imputed by carrying backward the first available post-dose observation.
3. The value at xx hours, if not exactly at xxh (or missing) and if not the last available observation, will be calculated based on linear interpolation between the last observed value before xxh and the first observed value after xxh.

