Based on the binary categorization:

- Detectable or quantifiable = Yes (1)
- Undetectable = No (0)

the difference in proportion of undetectable between each active treatment group as compared to placebo will be investigated. Frequency procedure in SAS® provides Newcombe confidence limits with Mantel-Haenszel weights for the common risk difference, controlling for the two randomization stratification factors (separately). The

difference in proportion of undetectable and 95% 2-sided confidence interval for this point estimate, controlling for randomization stratification factors, will be presented.

The aforementioned will be presented overall by treatment group and by the subgroups as defined in Section 2.4.

Time to Virus Undetectable [time to event]

With reference to the two time to event approaches, their definitions and derivations detailed in Section [5.3.1.1](#):

The time to event variables will be analyzed using Kaplan-Meier analysis (for both approaches). A summary table including number of subjects included in the analysis, number of subjects censored, 25th and 75th percentiles and median time to event, with 95% 2-sided confidence intervals based on Kaplan-Meier transformation method, will be presented by treatment group. The data will be presented graphically using the Kaplan-Meier estimate of the survival function by treatment group.

The aforementioned will be presented overall by treatment group and by the subgroups as defined in Section 2.4, for time (hours) to **confirmed undetectable** viral load only.

As sensitivity analysis, overall summary tables will be presented as described above for time (hours) to **confirmed undetectable** viral load but excluding nasal swab samples as previously described (refer to Section [5.2.3](#)).

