In addition to the Kaplan-Meier analysis, as described above, time (hours) to **confirmed undetectable** viral load and the differences in time to **confirmed undetectable** viral load of active dosing regimens versus placebo treatment, will also be estimated using the accelerated failure time (AFT) model, using the log-logistic distribution. The AFT model will include the categorical effects for treatment (with placebo as the reference), randomization stratification factors (derived) and baseline log₁₀ RSV RNA viral load as continuous covariate. A summary of information from the final AFT model will include parameter estimates and associated standard errors and covariance matrix of parameter estimates, estimated accelerated failure time ratios versus placebo and associated 95% 2-sided confidence intervals.

The aforementioned will be presented overall by treatment group and by the subgroups as defined in Section 2.4.

The parameter estimates and associated variance matrix resulting from AFT model, will be used in a generalized MCP-Mod approach that will test for existence of dose-response, at alpha=0.10 (1-sided). The aforementioned will be presented overall by treatment group only.

Graphical presentation will include:

- Overlay of survival curves with Kaplan-Meier survival function and AFT on one plot
- Forest plot of accelerated failure time ratios and resulting confidence intervals for subgroups of interest as defined in Section 2.4 including the relevant subgroup variable as covariate in the model with subgroup*treatment group interaction.

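### Target-not-detected is scored 0 log10 for both subtypes although the detection limits differ 7.75-fold, so RSV A and RSV B results are not comparable at low loads; subtype should be in the main models and a common-floor sensitivity analysis added

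*SAP*

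**What the plan says.** SAP 5.1.2 sets out the assay limits: "For the RSV A qRT-PCR assay, the LOD is 620 copies/mL and the LLOQ is 1000 copies/mL", and "For the RSV B qRT-PCR assay, the LOD is 80 copies/mL and the LLOQ is 250 copies/mL". A result that is detected but not quantifiable "will be imputed with the midpoint on the log scale between the limit of detection (LOD) and LLOQ" of its own assay, giving 2.90 log10 for RSV A and 2.15 for RSV B. For results that are not detected, the rule no longer depends on subtype: "for both RSV A and RSV B the value of TND will be imputed with" 0 log10.

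Table 16 (5.3.1.1) labels the lowest category "Undetectable (<LLOQ TND"), so undetectable means below 620 copies/mL for RSV A and below 80 for RSV B.

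The main viral-load models do not contain subtype:
- The primary MMRM (5.2.3) has "fixed (discrete) effect parameters for treatment, randomization stratification factors (derived), analysis visit and treatment-by-analysis visit interaction", plus baseline viral load and its interaction with visit.
- The Day 14 AUC model (5.3.2.1) has treatment, stratification factors and baseline viral load.
- The difference in proportion undetectable (5.3.2.1) is computed "controlling for the two randomization stratification factors (separately").
- For time to confirmed undetectable (5.3.2.1): "The AFT model will include the categorical effects for treatment (with placebo as the reference), randomization stratification factors (derived") and baseline viral load.

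Subtype does appear elsewhere. Table 8 (2.4) makes it a viral-load subgroup, and the subgroup models add it with its interactions. Section 5.3.2.1 lists it as a candidate in an exploratory backward regression, after which strong predictors may be tried as extra covariates in the primary model.

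The three sensitivity analyses in 5.2.3.1 change the source of the stratification factors, the analysis set, or drop swabs that are negative for RNase P and both subtypes. None changes the value given to an undetected result or the limit below which it applies.

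**The concern.** The plan recognises that the two assays differ when it imputes detected but non-quantifiable results, and ignores the difference when it imputes undetected ones. Two children with the same viral course can therefore have different recorded AUCs and different times to undetectable, only because one assay sees further down.

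Two things are at stake. In the pooled analysis, subtype becomes a source of variation that the main models leave in the residual, although subtype is determined at baseline. In the planned RSV A versus RSV B comparison, the higher RSV A limit converts more low values to 0, and it does so more often in the arm with lower loads. The drug could act identically on both subtypes and still show different recorded effects.

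**Working it through.** **Reproducing the plan's figures.** Midpoint = (log10 LOD + log10 LLOQ)/2.
- RSV A: (2.792 + 3.000)/2 = 2.896, stated as 2.90.
- RSV B: (1.903 + 2.398)/2 = 2.151, stated as 2.15.

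Both agree.

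**Gap between the limits.** 620/80 = 7.75; 2.792 − 1.903 = 0.889 log10.

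**Score for the same true load under 5.1.2.**

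| True copies/mL | RSV A | RSV B | B − A |
|---|---|---|---|
| 50 | 0 | 0 | 0 |
| 100 | 0 | 2.15 | 2.15 |
| 300 | 0 | 2.48 | 2.48 |
| 600 | 0 | 2.78 | 2.78 |
| 700 | 2.90 | 2.85 | −0.05 |
| 2000 | 3.30 | 3.30 | 0 |

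The large gap is confined to 80-620 copies/mL. From 620 to 1000 it is within about 0.11 log10, and from 1000 upward it is zero.

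**Weight in the AUC.** With daily sampling, an interior visit carries 24 h and the last visit 12 h. One interior sample at 100 to 600 copies/mL moves the AUC by 2.15 × 24 = 51.6 to 2.78 × 24 = 66.7 log10 copies.h/mL; an end sample moves it by half that. For scale, section 1.4 equates 105 with a 25% reduction, so the placebo AUC is about 105/0.25 = 420 and a 20% effect is 84.

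**One assumed course, start 5.0, falling 0.75 log10/day** (5.0, 4.25, 3.5, 2.75, 2.0):
- RSV A is recorded as 5.0, 4.25, 3.5, 0, 0: AUC = 24 × (2.5 + 4.25 + 3.5) = 246.
- RSV B is recorded as 5.0, 4.25, 3.5, 2.75, 2.15: AUC = 24 × (2.5 + 4.25 + 3.5 + 2.75 + 1.075) = 337.8.
- Gap 91.8.

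Over 12 such courses (start 5, 6 or 7 log10; decline 0.5, 0.75, 1.0 or 1.25 log10/day), the gap was 0 in six and 25.8 to 91.8 in the other six. With one floor for both subtypes it was 0 in all twelve. With each subtype's own LOD/2 in place of 0, it ran from +2 to −32, so that alternative shrinks the gap without removing it.

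**Treatment effect by subtype (simulation).** Assumptions: linear decline, mean baseline 5 to 6.5 log10 (SD 1, minimum 4.0), slope SD 0.3, noise SD 0.5, true AUC reduction 19-20%. Recorded reduction: 24-28% in RSV A and 21-23% in RSV B. Recorded AUC gap between subtypes at the same true course: 17-36 log10 copies.h/mL.

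**Time to undetectable.** At a decline of r log10/day, the RSV A child becomes undetectable 0.889/r days sooner: 1.8 days at r = 0.5, 0.9 at 1.0, 0.7 at 1.25.

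**Pooled comparison.** Assume a 50:50 subtype mix and 98 per arm (section 1.2). The SD of the between-arm difference in subtype share is √(2 × 0.25/98) = 0.071. Times 17-36, the typical chance shift is 1.2-2.6 log10 copies.h/mL, or 1.4-3.1% of 84. Subtype accounts for roughly 1-5% of residual AUC variance under the assumed trajectories. Taking 5% against Table 1's linear case (N = 74, CV 35%, power 92.3%, simulated MCP-Mod critical value 2.245): (1.43 + 2.245)/√0.95 − 2.245 = 1.53, a power of about 93.6%.

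**The case against.** The strongest reply is that treatment is randomized and every arm is scored by the same rule, so the pooled MCP-Mod test is not biased and the gain from a subtype term is about one point of power. That stands in full. A reader might infer a biased primary result, or set the 17-36 log10 copies.h/mL gap directly against the planned 84. Neither is supported: the gap is a contrast between subtypes and would become an arm difference only if the arms had opposite subtypes.

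A reader might also infer that subtype is in no model, or that the two AUCs are on different scales. The subgroup models contain subtype with interactions, the exploratory regression lists it, the units are the same, and scores coincide from 1000 copies/mL. What remains is that the main models omit it, and its route into the primary model is optional and data-driven.

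It is tempting to say that the planning figures in section 1.4 put expected Day 5 values at the floor. They do not. The SAP gives no baseline load, decline shape or frequency of undetected results, and a high below-limit rate follows only from fixing the AUC and assuming a straight line.

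The subgroup distortion is also modest against sampling error. With 49 per arm per subtype (assumed 50:50), the SE of the difference between two subtype effects is CV × √(4/49): 5.7 points at CV 20% and 10 at CV 35%. The study calls itself exploratory. This limits the urgency. It does not make the comparison like for like, and subtype in the subgroup model does not repair the floor.

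**Conclusion.** The concern holds in a limited form. The 7.75-fold (0.89 log10) difference in limits, the common 0 log10 score, the subtype-dependent meaning of undetectable, the absence of subtype from the four main viral-load analyses and the absence of any sensitivity analysis on the floor are all on the page and need no assumption.

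The consequences are of two kinds. For the pooled randomized comparison: no systematic bias, and a small loss of precision. For RSV A versus RSV B: AUC effect, proportion undetectable and time to undetectable are measured against different thresholds, so an apparent subtype difference of a few percentage points in AUC effect, or around a day in clearance, could come from the assays alone.

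The sizes rest on assumed linear declines, assumed baselines and an assumed even subtype mix. If few loads fall between 80 and 620 copies/mL by Day 5, the AUC effect vanishes; the unequal undetectability threshold remains.

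**What to change.** 1. In 5.2.3, add baseline RSV subtype (A, B, A+B) and subtype-by-visit to the primary MMRM. In 5.3.2.1, add subtype to the AFT model for time to confirmed undetectable. State this in advance in place of the data-driven option in 5.3.2.1, and say how a sparse A+B level is handled. This recovers precision; it does not remove the floor.

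2. In 5.2.3.1 and 5.3.2.1, add a sensitivity analysis with one common floor: RSV B results below 620 copies/mL are handled as RSV A target-not-detected, and 620 to 1000 as RSV A target-detected (2.90). Apply it to AUC through Day 5, proportion undetectable and time to undetectable, and use it whenever the subtype subgroups are compared. Keep the assay-specific limits in the main analysis.

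Cost: SAP wording, a few model parameters and one extra run of existing models. Subtype is already determined at baseline. RSV B detections between 80 and 620 copies/mL are given up in the sensitivity analysis only. Redefining undetectable for the main analysis is a trade-off that this point does not require, and a left-censored repeated-measures model is more work than one extra run, because the REML model with Kenward-Roger degrees of freedom does not accommodate censoring.
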